Clinical Study Protocol

A Study to EXhibit Percutaneous coronary Artery dilatation with Non-Slip Element balloon (EXPANSE-PTCA)

Study Protocol Number: RDX-CL-5000

Revision: B, 03Dec2021

ClinicalTrials.gov Identifier: NCT04985773

Infraredx, Inc.
[name]
[name]
[contact]

THIS STUDY PROTOCOL CONTAINS CONFIDENTIAL INFORMATION FOR USE BY THE INVESTIGATORS AND THEIR DESIGNATED REPRESENTATIVES PARTICIPATING IN THE STUDY. IT SHOULD BE HELD CONFIDENTIAL AND MAINTAINED IN A SECURE LOCATION. IT SHOULD NOT BE COPIED OR MADE AVAILABLE FOR REVIEW BY ANY UNAUTHORIZED PERSON OR FIRM.

Sponsor Signatures

Signature:

DocuSigned by [name]
 [name] | I approve this document
12/3/2021 | 11:05:29 AM PST
2712E3A440FB494181A6307E01D3DE74

Date:

12/3/2021

Sponsor

[name], Senior Vice President of Clinical, Research & Regulatory, Infraredx

Signature:

DocuSigned by [name]
 [name] | I have reviewed this document
12/3/2021 | 11:06:41 AM PST
5CDF39EA018543A5B2DBDF3EB3F1641B

Date:

12/3/2021

CRO

[name], Clinical Study Lead, BRIGHT Research Partners

Signature:

DocuSigned by [name]
 [name] | I approve this document
12/3/2021 | 11:11:30 AM PST
B9331EF4F03B4104A7B59288D638B192

Date:

12/3/2021

CRO

[name], Chief Scientific Strategist, BRIGHT Research Partners

Principal Investigator Signature

I have read the clinical study protocol and agree to adhere to the requirements of this protocol in accordance with the ICH guidelines for good clinical practices, ISO 14155, and applicable FDA regulations.

Printed Name:

Site #:

Signature:

Date:

 CLINICAL STUDY PROTOCOL SYNOPSIS Infraredx Study Number: RDX-CL-5000	
Study Title	A Study to EXhibit Percutaneous coronary Artery dilatation with Non-Slip Element balloon (EXPANSE-PTCA)
Identifying Regulatory Numbers	FDA IDE number – G210195 Clinicaltrials.gov – NCT 04985773
Study Objective	To evaluate safety and effectiveness of the Lacrosse NSE ALPHA coronary dilatation catheter during percutaneous coronary intervention in subjects with stenotic coronary arteries.
Device Description	
The Lacrosse NSE ALPHA is a rapid exchange percutaneous transluminal coronary angioplasty balloon catheter with non-slip element nylon threads that focus dilatation force to reduce balloon slippage during inflation. The three nylon threads are 0.39 mm in height, located at 120° intervals parallel to the shaft, and bonded at the distal and proximal ends of the 13 mm long semi-compliant balloon. Inside the balloon, two radiopaque markers indicate the working length of the balloon to guide proper positioning in the targeted lesion. A hydrophilic coating is applied to the catheter shaft and tapered distal tip. The proximal shaft contains catheter insertion depth markers at 93 cm and 103 cm, and the proximal hub enables balloon inflation and deflation using a standard inflation device. The 2.7 Fr catheter is compatible with 0.014" guidewires and the 13 mm long semi-compliant balloon is available in eight diameters ranging from 2.0 mm to 4.0 mm.
 
Note: The Lacrosse NSE ALPHA is approved for marketing in 28 countries and the European Union.

Proposed Device Indications for Use	The Lacrosse NSE ALPHA coronary dilatation catheter is indicated for balloon dilatation of the stenotic portion of the coronary artery including both de novo and in-stent restenosis, for the purpose of improving myocardial perfusion. This device is also indicated for the post-delivery expansion of balloon expandable stents.
Study Design	Prospective, multi-center, single arm clinical study. Subjects will be followed through hospital discharge.
Number of Sites & Subjects	200 subjects will be treated at up to 15 investigational sites in the U.S., including a minimum of 30 subjects with in-stent restenosis. Enrollment will continue until both the overall target of 200 and the ISR cohort of 30 have been obtained. No single site will enroll more than 20% of the total enrollment.
Study Population	Patients with stenotic coronary artery disease.
Primary Endpoint	
Device procedural success, defined as:
 
Successful delivery, inflation, deflation, and withdrawal of the study balloon; andNo evidence of device-related vessel perforation, flow limiting dissection (grade C or higher per Clinical Events Committee (CEC) adjudication) or reduction in thrombolysis in myocardial infarction (TIMI) flow from baseline (per core laboratory assessment); andFinal TIMI flow grade of 3 at the conclusion of the PCI procedure per core laboratory assessment.

 A NIPRO COMPANY		CLINICAL STUDY PROTOCOL SYNOPSIS Infraredx Study Number: RDX-CL-5000
		This endpoint will be presented as the proportion of subjects experiencing device procedural success. The proportion of target lesions meeting the primary endpoint will be concurrently calculated and presented as a secondary endpoint, as noted below
Secondary Endpoints	
1. Angiographic procedural success, defined as final diameter stenosis ≤50% in at least one of the Lacrosse NSE ALPHA attempted lesions following completion of the interventional procedure, including adjunctive stenting per core laboratory assessment.2. Major adverse cardiac events (MACE) through hospital discharge per CEC adjudication. MACE is defined as a composite of:
• All-cause death• Myocardial infarction• Clinically indicated target lesion revascularization3. Stent thrombosis within the target vessel(s) through hospital discharge using ARC-2 definitions for definite & probable, per CEC adjudication.4. Clinically significant arrhythmia (defined as those requiring intervention) through hospital discharge, per CEC adjudication.5. Occurrence of Lacrosse NSE ALPHA balloon rupture, per device deficiency eCRF.6. Change in minimum lumen diameter following use of Lacrosse NSE ALPHA catheter, measured by quantitative coronary angiography per core laboratory assessment.7. Device procedural success defined as for the primary endpoint, calculated and presented per target lesion. 
Secondary endpoints 1 through 5 are defined at a subject level and will be presented as the proportion of subjects experiencing the above events. In cases where multiple events per subject may be observed (e.g., adverse events), the primary analysis will be at the subject level but total event counts will also be reported. Secondary endpoints 6 and 7 are defined at the lesion level and statistical analyses of these endpoints will account for within-subject correlation as some subjects will have more than one target lesion, using generalized estimating equations with an exchangeable correlation structure.
	
Study Eligibility Criteria	
Subjects must meet all the following inclusion criteria:
 
General inclusion criteria
 
1. Age 18 years or older.2. Willing to provide written informed consent and written HIPAA authorization prior to initiation of study-related procedures.3. Agree to not participate in any other clinical study, during hospitalization for the index procedure that would interfere with the endpoints of this study.4. Clinical evidence of ischemic heart disease, stable/unstable angina, or silent ischemia.5. Acceptable candidate for PCI and emergency coronary artery bypass grafting and is planned for possible PTCA and/or stent placement.	

 A NIPRO COMPANY		CLINICAL STUDY PROTOCOL SYNOPSIS Infraredx Study Number: RDX-CL-5000

Angiographic inclusion criteria
 
6. De novo or restenotic lesion(s) in native coronary arteries, including in-stent restenosis.
 
7. A maximum of two lesions, including at least one target lesion, in single or double vessel coronary artery disease.
 
a) If two target lesions are defined, then no non-target lesions can be treated.b) If a single target lesion is defined, then a single non-target lesion may be treated, but if so, it must be located in a different coronary artery from the target lesion. 
8. Target lesion(s) must have a reference vessel diameter between 2.0 mm and 4.0 mm by visual estimation.
 
9. Target lesion(s) must have a diameter stenosis of (a) $\geq 70\%$ by visual estimation or (b) $> 50\%$ by visual estimation and a fractional flow reserve (FFR) of < 0.80 or resting full-cycle ratio (RFR) or instantaneous wave-free ratio (iFR) < 0.9.
 
10. Treatment of non-target lesion, if any, must be completed prior to treatment of target lesion; must not, in the opinion of the investigator, impact the conduct or completion of the index procedure; and must be deemed a clinical angiographic success as visually assessed by the investigator.
 
Subjects must not meet any of the following exclusion criteria:
 
General exclusion criteria
 
1. Known hypersensitivity or contraindication to aspirin, heparin, bivalirudin, anti-platelet medications, a clopidogrel non-responder, or sensitivity to contrast media that cannot be adequately pre-medicated or replaced with a clinically suitable alternative.2. Known diagnosis of type I myocardial infarction (resulting from primary reduction of flow from a culprit lesion likely to have a thrombotic component) within 7 days prior to the index procedure.3. Known pregnancy or is nursing. Women of child-bearing potential should have a documented negative pregnancy test within 7 days prior to index procedure.4. Planned target lesion treatment with atherectomy (rotational, orbital or laser), cutting balloon, thrombectomy, lithotripsy or an unapproved device during the index procedure.5. Serum creatinine > 2.0 mg/dl within 7 days prior to the index procedure.6. Cerebrovascular accident within 6 months prior to the index procedure.7. Active peptic ulcer or active gastrointestinal bleeding within 6 months prior to the index procedure.8. Left ventricular ejection fraction $< 30\%$ based on most recent measurement within a year of the index procedure (if LVEF is not available in the medical records, it may be obtained at the time of the index procedure, prior to enrollment).9. Target lesion located within a bypass graft (venous or arterial) or graft		

 A  NIPRO COMPANY		CLINICAL STUDY PROTOCOL SYNOPSIS Infraredx Study Number: RDX-CL-5000
		
anastomosis.
 
10. Previous percutaneous intervention, within 9 months before the study procedure, on lesions in a target vessel (including side branches) that are located within 10 mm from the current target lesion.
 
11. Target lesion(s) with complete total occlusion (CTO) defined as the complete obstruction of a native coronary artery, exhibiting TIMI 0 or TIMI 1 flow, with an occlusion duration of at least 3 months.
 
12. Unstable hemodynamics or shock.
 
13. Other medical condition which might, in the opinion of the investigator, put the patient at risk or confound the results of the study.
 
Angiographic exclusion criteria
 
14. Target lesion(s) longer than 32 mm by visual estimation.
 
15. Extreme angulation (90° or greater) within 5 mm of the target lesion.
 
16. Target lesion(s) demonstrating flow limiting dissection (NHLBI Grade C or higher) prior to deployment of the Lacrosse NSE ALPHA.
 
17. Unprotected left main coronary artery disease (>50% diameter stenosis).
 
18. Coronary artery spasm of the target vessel in the absence of a significant stenosis.
 
19. Target lesion(s) with angiographic presence of probable or definite thrombus.
 
20. Target lesion(s) involves a bifurcation requiring treatment with more than one stent or pre-dilatation of a side branch >2.0 mm in diameter.
 
21. Target lesion(s) located in bifurcation beyond stent struts.
 
22. Target lesion(s) located distal to an implanted stent.
 
23. Target lesion(s) with stent damage.
 
24. Non-target lesion that meets any of the following criteria:
 
• Located within a bypass graft (venous or arterial)• Located in an unprotected left main coronary artery• A CTO• Involves a bifurcation
Study Duration	Enrollment is expected to take approximately 12 months. Each study subject will actively participate in the study through hospital discharge. The overall study duration, from subject enrollment through final report, is expected to be approximately 18-24 months.	
Study Sponsor	Infraredx, Inc. [name] [contact]	
National Principal Investigator	[name] Professor of Medicine Duke University School of Medicine	

 A  NIPRO COMPANY	CLINICAL STUDY PROTOCOL SYNOPSIS Infraredx Study Number: RDX-CL-5000

1.0 ABBREVIATIONS

The following is a list of abbreviations used in the body of this document. Abbreviations solely used in tables (e.g., table headers) are described in the table footer and are not included below.

Abbreviation	Description
BMS	bare metal stent
CABG	coronary artery bypass grafting
CEC	Clinical Events Committee
CFR	Code of Federal Regulations (U.S.)
CRF/eCRF	case report form / electronic case report form
CRO	clinical research organization
CTO	chronic total occlusion
DES	drug-eluting stent
EDC	electronic data capture (database)
FDA	Food and Drug Administration (U.S.)
GCP	Good Clinical Practice
HIPAA	Health Insurance Portability and Accountability Act
ICF	informed consent form
ICH	International Conference on Harmonisation
IFU	instructions for use
IRB	Institutional Review Board
ISO	International Organization for Standardization
ISR	in-stent restenosis
LVEF	left ventricular ejection fraction
MACE	major adverse cardiac events
MI	myocardial infarction
MLD	minimum lumen diameter
NHLBI	National Heart, Lung, and Blood Institute
NSE	non-slip element
NSTEMI	Non-ST-elevation myocardial infarction
PCI	percutaneous coronary intervention
PI	principal investigator
PG	performance goal
PTCA	percutaneous transluminal coronary angioplasty
QCA	quantitative coronary angiography
RVD	reference vessel diameter

Abbreviation	Description
RX	rapid exchange
SAE	serious adverse event
ST	stent thrombosis
STEMI	ST-elevation myocardial infarction
TIMI	thrombolysis in myocardial infarction
TLR	target lesion revascularization
UADE	unanticipated (serious) adverse device effect

The remainder of this page is intentionally blank

2.0 CLINICAL BACKGROUND

Percutaneous coronary intervention (PCI) has evolved over the past 20 years from simple balloon angioplasty for treating atherosclerotic plaques in arteries to more progressive treatments, such as coronary stents, laser therapy, and radiation therapy. Two treatments remain in the forefront of interventional cardiology: percutaneous transluminal coronary angioplasty (PTCA) and coronary stenting. PTCA is a therapeutic technique to dilate occlusive lesions of the coronary artery. Application of this technique requires tools including PTCA balloon catheters, guiding catheters, guidewires, balloon inflation devices, and catheter introducers, as well as equipment such as cineradiographic X-ray machines, also referred to as fluoroscopy.

A PTCA balloon may be used in patients with acute myocardial infarction to treat calcified lesions, restenotic lesions, and intra-stent stenosis, and to perform predilatation for drug-eluting stents (DES) and bare metal stents (BMS). While BMS treatment dramatically reduces the incidence of dissection, elastic recoil, and remodeling, the concern of interest becomes in-stent restenosis (ISR), often leading to revascularization. DES therapy has subsequently led to a substantial reduction in the incidence of ISR, but ISR nevertheless remains among the consequential potential sequelae (Singh).

Heavily calcified lesions – markers of advanced atherosclerosis that are correlated with multivessel coronary disease and complex lesions – present a challenge for PTCA and stenting procedures due to their “higher risk of immediate complications, late failure due to stent under expansion and malapposition, and consequently poor clinical outcome” (Dini). According to Dini, the prevalence of moderate and severe calcific coronary stenoses ranges between 18% and 26%, and these lesions “are a predictor of a worse clinical outcome, associated with higher mortality, major adverse cardiovascular events (MACE) and target vessel failure on multivariate analysis after correction for confounders” (Dini).

With traditional semi-compliant PTCA balloon catheters, calcified lesions can cause the balloon to form a dog-bone shape, creating excessive pressures at the balloon edges that can cause coronary dissections or perforations (Dini). One method to avoid this dog-bone effect is the use of non-compliant balloons, which allow for higher inflation pressures and provide higher forces in a focal segment of the target lesion. Traditional non-compliant balloon catheters do not, however, contain mechanisms to prevent slippage of the balloon. Such slippage (frequently termed “watermelon seeding”) can have damaging effect on the artery and consequently lead to undesirable outcomes (Singh).

Cutting balloons, such as the Flextome Cutting Balloon introduced by Boston Scientific in 1991, provided another innovation aimed at addressing the challenges in treating calcified coronary lesions. These devices contain longitudinal microblades on the surface of the balloon that cut the inner surface of the vessel, reducing recoil, minimizing neointima proliferation, and reducing balloon slippage. Due to high crossing profiles and unfavorable clinical results, including a significantly higher perforation rate, the European Society of Cardiology and American College

of Cardiology guidelines have discouraged the use of cutting balloons, with the exception of restricted applications for resistant lesions (Dini).

Scoring balloons, with their semi-compliant balloons encircled by scoring elements, are smaller profile devices than cutting balloons, and because they can be fully expanded with a low inflation pressure, Dini notes that they produce “less trauma to vessel walls and a minor risk of coronary dissections” (Dini).

Several scoring balloon catheters have been commercially available to treat mild to moderate calcified lesions, including the AngioSculpt (Spectranetics-Philips), Flextome and Wolverine (Boston Scientific), Chocolate (QT Vascular/Medtronic/Teleflex), Fx miniRAIL (Guidant, no longer manufactured), and Scoreflex (OrbusNeich Medical).

The Lacrosse NSE ALPHA coronary dilatation catheter, which has been available in markets outside the U.S. since 2013, is a rapid exchange (RX) semi-compliant balloon catheter with nylon thread elements designed to limit the occurrence of balloon slippage. This study is intended to evaluate safety and effectiveness of the Lacrosse NSE ALPHA during PCI in subjects with stenotic coronary arteries.

3.0 TREATMENT DESCRIPTION

3.1 Device Description

The Lacrosse NSE ALPHA coronary dilatation catheter is a rapid exchange (RX) PTCA balloon catheter with non-slip element (NSE) nylon threads that focus dilatation force to reduce balloon slippage during inflation (**Figure 1**). The three nylon threads are 0.39 mm in height, located at 120° intervals parallel to the shaft, and bonded at the distal and proximal ends of the 13 mm long semi-compliant balloon (**Figure 2**). Inside the balloon, two radiopaque markers indicate the working length of the balloon to guide proper positioning in the target lesion.

The distal section of the 2.7 Fr catheter comprises a dual-lumen shaft; the outer lumen is for balloon dilatation, and the inner lumen allows for rapid exchange of 0.014" or smaller guidewires. A hydrophilic coating is applied to the catheter shaft and tapered distal tip. The proximal shaft contains catheter insertion depth markers at 93 cm and 103 cm, and the proximal hub enables balloon inflation and deflation using a standard balloon inflation device.

The device is available in eight balloon diameters ranging from 2.0 mm to 4.0 mm (**Table 1**). The nominal inflation pressure is 6 atm and the rated burst pressure is 14 atm. A balloon compliance chart is provided in the device instructions for use (IFU). The device is packaged sterile with a balloon protective tube and stylet that are removed prior to use.

Figure 1: Lacrosse NSE ALPHA

[figure not shown]

Figure 2: Non-Slip Element (NSE) Nylon Threads

[figure not shown]

Table 1: Lacrosse NSE ALPHA Model Numbers

Model #	Balloon size
NSA20013	2.00 mm x 13 mm
NSA22513	2.25 mm x 13 mm
NSA25013	2.50 mm x 13 mm
NSA27513	2.75 mm x 13 mm
NSA30013	3.00 mm x 13 mm
NSA32513	3.25 mm x 13 mm
NSA35013	3.50 mm x 13 mm
NSA40013	4.00 mm x 13 mm

3.1.1 Device Manufacturer

The study sponsor and initial importer of the Lacrosse NSE ALPHA is Infraredx, Inc. (Bedford, MA). The device is manufactured by Goodman Co., Ltd. (Nagoya, Japan).

The Lacrosse NSE ALPHA is approved for marketing in 28 countries and the European Union.

3.1.2 Device Labeling / Instructions for Use

The IFU will be provided with each investigational device.

3.2 Principle of Operation / Mechanism

The Lacrosse NSE ALPHA is prepared and used similarly to standard commercially available PTCA balloon catheters. The catheter is guided over a 0.014" guidewire to the target lesion, and the balloon is inflated and deflated using a standard balloon inflation device filled with contrast media. The nylon NSE elements that are located over the balloon have a scoring effect that focuses dilatation force to reduce balloon slippage during inflation.

3.3 Proposed Indications for Use

The Lacrosse NSE ALPHA coronary dilatation catheter is indicated for balloon dilatation of the stenotic portion of the coronary artery including both *de novo* and in-stent restenosis, for the purpose of improving myocardial perfusion. This device is also indicated for the post-delivery expansion of balloon expandable stents.

4.0 OBJECTIVE

The objective of this study is to evaluate safety and effectiveness of the Lacrosse NSE ALPHA coronary dilatation catheter during PCI in subjects with stenotic coronary arteries.

5.0 ENDPOINTS

Endpoints selected for this trial, including the primary endpoint, are common measures of safety and effectiveness for comparable devices in the population under study; in particular, the primary endpoint is identical or nearly identical to recent/ongoing regulatory studies of the Scoreflex NC, Sapphire II PRO, Emerge, Mini Trek RX, and Sprinter Legend balloon catheters.

5.1 Primary Endpoint

The primary endpoint for the study is device procedural success, defined as:

- Successful delivery, inflation, deflation, and withdrawal of the study balloon; and
- No evidence of device-related vessel perforation, flow limiting dissection (grade C or higher, per Clinical Events Committee (CEC) adjudication) or reduction in thrombolysis in myocardial infarction (TIMI) flow from baseline (per core laboratory assessment); and
- Final TIMI flow grade of 3 at the conclusion of the PCI procedure per core laboratory assessment.

This endpoint will be presented as the proportion of subjects experiencing device procedural success. The proportion of target lesions meeting the primary endpoint will be concurrently calculated and presented as a secondary endpoint, as noted below.

5.2 Secondary Endpoints

The secondary endpoints for the study are:

1. Angiographic procedural success, defined as final diameter stenosis $\leq 50\%$ in at least one of the Lacrosse NSE ALPHA attempted lesions following completion of the interventional procedure, including adjunctive stenting per core laboratory assessment.
2. MACE through hospital discharge per CEC adjudication. MACE is defined as a composite of:
 - All-cause death
 - Myocardial infarction (MI)
 - Clinically indicated target lesion revascularization (TLR)
3. Stent thrombosis (ST) within the target vessel(s) through hospital discharge using ARC-2 definitions for definite & probable, per CEC adjudication.
4. Clinically significant arrhythmia (defined as those requiring intervention) through hospital discharge, per CEC adjudication.
5. Occurrence of Lacrosse NSE ALPHA balloon rupture, per device deficiency eCRF.
6. Change in minimum lumen diameter (MLD) following use of the Lacrosse NSE ALPHA catheter, measured by quantitative coronary angiography (QCA) per core laboratory assessment.
7. Device procedural success defined as for the primary endpoint, calculated and presented per target lesion.

Secondary endpoints 1 through 5 are defined at a subject level and will be presented as the proportion of subjects experiencing the above events. In cases where multiple events per subject may be observed (e.g., adverse events), the primary analysis will be at the subject level but total event counts will also be reported. Secondary endpoints 6 and 7 are defined at the lesion level and statistical analyses of these endpoints will account for within-subject correlation as some subjects will have more than one target lesion, using generalized estimating equations with an exchangeable correlation structure.

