6.5 Subject Eligibility Criteria

6.5.1 Inclusion Criteria

Subjects must meet all the following inclusion criteria:

General inclusion criteria

1. Age 18 years or older.
2. Willing to provide written informed consent and written Health Insurance Portability and Accountability Act (HIPAA) authorization prior to initiation of study-related procedures.
3. Agree to not participate in any other clinical study, during hospitalization for the index procedure, that would interfere with the endpoints of this study.
4. Clinical evidence of ischemic heart disease, stable/unstable angina, or silent ischemia.
5. Acceptable candidate for PCI and emergency coronary artery bypass grafting (CABG) and is planned for possible PTCA and/or stent placement.

Angiographic inclusion criteria

6. *De novo* or restenotic lesion(s) in native coronary arteries, including in-stent restenosis.
7. A maximum of two lesions, including at least one target lesion, in single or double vessel coronary artery disease.
 - a. If two target lesions are defined, then no non-target lesions can be treated.

- b. If a single target lesion is defined, then a single non-target lesion may be treated, but if so, it must be located in a different coronary artery from the target lesion.
- 8. Target lesion(s) must have a reference vessel diameter (RVD) between 2.0 mm and 4.0 mm by visual estimation.
- 9. Target lesion(s) must have a diameter stenosis of (a) $\geq 70\%$ by visual estimation or (b) $>50\%$ by visual estimation and a fractional flow reserve (FFR) of <0.80 or resting full-cycle ratio (RFR) or instantaneous wave-free ratio (iFR) <0.9 .
- 10. Treatment of non-target lesion, if any, must be completed prior to treatment of target lesion; must not, in the opinion of the investigator, impact the conduct or completion of the index procedure; and must be deemed a clinical angiographic success as visually assessed by the investigator.

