7.5 Treatment Procedure & Immediate Post-Procedure Assessment

The PCI procedure will be performed following these guidelines:

- A maximum of one non-target lesion, if identified, must be located in a different coronary artery from the target lesion and must be treated first and deemed a clinical angiographic success, as visually assessed by the physician. Study devices cannot be used on this non-target lesion.
- Target lesion will be treated using the Lacrosse NSE ALPHA following the device instructions for use.
- A target lesion composed of multiple focal lesions that can be covered with one stent will be considered as a single lesion.
- A separate Lacrosse NSE ALPHA study device must be used for treatment of each target lesion.

Additional procedures and interventions may be performed per standard of care at the discretion of the treating investigator (except those defined in the exclusion criteria).

Post-procedure angiographic imaging of the target lesion must be captured and performed per the instructions provided by the core laboratory and must be captured in the same precise manner as was used for the pre-procedure images. Angiographic images must be sent to the core lab following the instructions provided by the core laboratory.

Standard PCI procedural data will be collected on the eCRFs, such as:

- Vessel and lesion characteristics, including MLD and diameter stenosis (%)
- TIMI grade flow pre- and post-treatment
- Type and size of study devices used, including lot number
- Device performance assessment, including balloon slippage
- Procedural durations, including start/end times
- Air kerma (Gy) and total fluoroscopy time

- Adverse event assessment, including perforation and dissection classifications
- Device deficiency assessment

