### 7.1. Descriptive Statistics

Continuous data will be summarized using descriptive statistics: mean, standard deviation, median, and range or interquartile range. Categorical variables will be summarized using frequency counts and percentages. For endpoints analyzed at the subject level that can occur more than once in a single subject, such as adverse events, the percentage will be based on the number of subjects experiencing the event; both subject and event counts will be reported. For endpoints analyzed at the lesion level (secondary endpoints 6 and 7 as defined above), the lesion-level analysis will be considered primary.

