## **9.2. Secondary Endpoints**

Secondary endpoints 1 through 5 (as stated and numbered above) are defined at a subject level and will be presented as the proportion of subjects experiencing the above events. In cases where a subject-level analysis is specified but multiple events per subject may be observed (e.g., adverse events), the primary analysis will be at the subject level but total event counts will also be reported. Secondary endpoints 6 and 7 are defined at the lesion level and statistical analyses of these endpoints will account for within-subject correlation as some subjects will have more than one target lesion. For these endpoints, generalized estimating equations will be applied, using an exchangeable (within-subject) correlation structure.

Secondary endpoints defined as continuous measures (e.g., MLD) will be summarized according to the general principles stated above.

Secondary endpoints as defined in this protocol are not intended for labeling claims and hence no formal statistical hypotheses are defined *a priori*. Multiplicity of testing and associated alpha allocation (i.e., between the primary and secondary endpoints) is therefore not applicable to the current investigation.

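### Does secondary endpoint 1 mislead by counting a two-lesion subject as an angiographic success when only one lesion reaches 50% stenosis or less?

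*Protocol*

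**What the plan says.** Protocol 5.2 defines angiographic procedural success as a final diameter stenosis of 50% or less "in at least one of the Lacrosse NSE ALPHA attempted lesions following completion of the interventional procedure", with adjunctive stenting included and the core laboratory as assessor. The Protocol synopsis and SAP 6.2 use the same rule. Protocol 13.2 repeats it without naming the assessor. The endpoint is reported as a proportion of subjects.

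Two target lesions are possible. Inclusion criterion 7 in Protocol 6.5.1 says "If two target lesions are defined, then no non-target lesions can be treated", and Protocol 5.2 expects that some subjects will have more than one.

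Two secondary endpoints are analysed per lesion. SAP 9.2 says "Secondary endpoints 6 and 7 are defined at the lesion level and statistical analyses of these endpoints will account for within-subject correlation", and SAP 7.1 adds "For endpoints analyzed at the lesion level (secondary endpoints 6 and 7 as defined above), the lesion-level analysis will be considered primary". Endpoint 6 is "Change in minimum lumen diameter (MLD) following use of the Lacrosse NSE ALPHA catheter". Endpoint 7 applies the primary endpoint's criteria to each target lesion: balloon use, perforation, dissection, loss of TIMI flow, and "Final TIMI flow grade of 3 at the conclusion of the PCI procedure per core laboratory assessment".

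Protocol 8.4 and SAP 9.2 state that the secondary endpoints are not intended to support labeling and carry no formal hypotheses.

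**The concern.** A subject with one lesion at 50% or less and another above 50% is reported as a success. The lesion-level endpoints do not explicitly show the second lesion's residual stenosis. Endpoint 6 is a change in lumen diameter with no percentage threshold, and endpoint 7 has no stenosis criterion. The ancillary data in Protocol 5.3 and the summaries in SAP section 8 add no table of final stenosis by lesion.

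The reported rate can therefore never be lower than the rate that requires every attempted lesion to succeed. A reader may be unable to recover the difference from the tables the plan names. If the gap were large, or if a claim or decision rested on this endpoint, the effectiveness result would look better than the lesion results justify.

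**Working it through.** **1. The plan's own figure.** No design figure is stated for endpoint 1. The only one is the primary endpoint's power (Protocol 8.6, SAP 10): exact one-sided binomial test, alpha 0.05, performance goal 87.7%, assumed success rate 93.5%.

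- With 200 subjects, the smallest passing count is 184, the exact alpha is 0.0351 and the power is 84.3%. The stated 84% reproduces.
- With 190 subjects (5% missing), the passing count is 175 and the power is 82.5%. The stated figure of above 80% holds.

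The primary endpoint contains no stenosis criterion, so the rule for endpoint 1 does not enter this calculation.

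**2. Is the rule consistent?** The synopsis, Protocol 5.2, Protocol 13.2 and SAP 6.2 all require success in at least one attempted lesion. An analyst following either document computes the same number. There is no contradiction and no ambiguity about how a two-lesion subject is scored.

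**3. How far could the two rates differ?** Let w be the share of subjects with two attempted lesions, p the per-lesion success rate and rho the within-subject correlation. The documents give none of these, so all three are assumed. The formula also assumes the same p in one-lesion and two-lesion subjects.

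- P(both lesions succeed) = p² + rho·p(1 − p)
- P(at least one succeeds) = 2p − P(both)
- At-least-one rate = (1 − w)p + w·P(at least one)
- All-lesions rate = (1 − w)p + w·P(both)
- Gap = 2w(1 − rho)p(1 − p)

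Worked case, w = 0.10, p = 0.95, rho = 0.3:

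- P(both) = 0.9025 + 0.3 × 0.0475 = 0.91675
- P(at least one) = 1.90 − 0.91675 = 0.98325
- At-least-one rate = 0.855 + 0.098325 = 95.33%
- All-lesions rate = 0.855 + 0.091675 = 94.67%
- Gap = 2 × 0.10 × 0.7 × 0.0475 = 0.665 points, or 1.33 of 200 subjects

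| w | p | rho | Gap (points) | Subjects of 200 |
|---|---|---|---|---|
| 0.05 | 0.99 | 0.5 | 0.05 | 0.10 |
| 0.05 | 0.98 | 0.5 | 0.10 | 0.20 |
| 0.10 | 0.99 | 0.3 | 0.14 | 0.28 |
| 0.10 | 0.98 | 0.3 | 0.27 | 0.55 |
| 0.10 | 0.95 | 0.3 | 0.67 | 1.33 |
| 0.20 | 0.95 | 0.3 | 1.33 | 2.66 |
| 0.20 | 0.95 | 0 | 1.90 | 3.80 |
| 0.30 | 0.90 | 0 | 5.40 | 10.80 |

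The last row needs three unfavourable inputs together: 30% two-lesion subjects, one lesion in ten left above 50%, and no correlation between lesions in the same subject.

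**4. What depends on the gap?** Endpoint 1 has no hypothesis, no threshold to pass and no share of alpha. Neither document attaches a decision to it. At any row of the table, the trial's formal conclusion is the same.

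**5. Are the lesion data lost?** No. Protocol 7.5 has sites record "Vessel and lesion characteristics, including MLD and diameter stenosis", and also requires that "Post-procedure angiographic imaging of the target lesion must be captured and performed per the instructions provided by the core laboratory". SAP section 1 expects analyses beyond those pre-specified. A count of two-lesion subjects with one lesion above 50% can be produced without new data.

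**The case for a change.** The factual core of the concern is right. No output is explicitly specified that shows a second lesion against the 50% threshold. The plan reports its other success measure, device procedural success, both per subject and per lesion, so the absence of a lesion-level companion here looks uneven. Permission for additional analyses is not a commitment to run this one, and a row fixed beforehand is more credible than one chosen after the results are known. Because w, p and rho are all unknown, a small gap cannot be guaranteed.

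A possible answer is the statement in Protocol 5.2 and 8.4 and SAP 9.2 that total event counts will accompany subject-level results where a subject can have several events. I do not rely on it. Its example is adverse events, endpoint 1 is binary per subject, and no lesion denominator is named.

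What stands is that an all-lesions figure would be informative and cheap. That does not make the planned figure wrong. The rule is part of the endpoint's definition, so a reader who sees the definition knows that one successful lesion is enough. Pre-specification also protects little for a descriptive count with no test attached.

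**Conclusion.** The concern does not hold as a fault in the plan. The at-least-one rule is a declared and consistent design choice. Applied as written, it gives a correct figure for the endpoint as defined, and the endpoint supports no test, claim or decision. The 84% power for the primary endpoint reproduces and is unaffected.

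The difference from an all-lesions rate is about 0.3 to 1.3 of 200 subjects in the middle cases (w = 10%, rho = 0.3, p = 0.95 to 0.99). Across all the assumptions shown it runs from 0.1 to 10.8 subjects. These sizes rest entirely on assumed inputs and on equal success rates in one-lesion and two-lesion subjects. The conclusion does not rest on them: it follows from the endpoint's explicit definition and descriptive role. A companion row for two-lesion subjects is a matter of reporting preference.
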